3. INVESTIGATIONAL PLAN

3.1. Overall Study Design

The study is a multicenter, adaptive, randomized, double-blinded and placebo-controlled Phase II/III trial, and will be conducted at selected investigational sites globally.

Phase II part will evaluate the efficacy, safety, and PK of SCTA01 15 mg/kg, 50 mg/kg in patients with severe COVID-19. The primary endpoint will evaluate TTCI in study group 1 [SCTA01 15 mg/kg + best supportive care (BSC)], study group 2 (SCTA01 50 mg/kg + BSC) and control group (placebo + BSC) up to Day 29. The secondary endpoint will evaluate the virologic efficacy in study group 1 (SCTA01 15 mg/kg +BSC), study group 2 (SCTA01 50 mg/kg + BSC) and the control group (placebo + BSC) from baseline to Day 8, and then determine the recommended dose for Phase III part.

In the Phase II part of the study, 285 subjects will be randomized by 1:1:1 ratio to 15 mg/kg group, 50 mg/kg group and placebo group, with 95 subjects in each group.

At the end of Phase II part, enrollment will be paused and an interim analysis for dose selection will be performed after the 285th subject has been observed for TTCI. An IDMC will assess the benefit and risk to decide the dose for Phase III part of the part.

Enrollment will be resumed and the study continue into Phase III part after the IDMC has completed the evaluation and recommended the dose for Phase III part.

The Phase III part will evaluate the efficacy, safety, and immunogenicity of SCTA01 at the dosage recommended by the IDMC (X mg/kg or X mg) in severe patients with COVID-19. The primary endpoint will evaluate TTCI (8-point ordinal scale) in study group (SCTA01 X mg/kg or X mg + BSC) and control group (placebo + BSC) up to Day 29.

Approximately 510 subjects in Phase III part will be randomized by 1:1 ratio to SCTA01 (X mg/kg or X mg) and placebo, with 255 subjects in each group. The IDMC will be used to monitor safety and efficacy information.

Total number of subjects in the study is about 795.

Interim analysis (IA): There will be three un-blinded interim analyses when 143rd patient in Phase II has completed Day 8 visit, at the end of Phase II and when the 160th patient in Phase III has completed Day 29 or Early Withdraw visit.

- The 1st interim analysis is for safety evaluation. Only safety data will be reviewed at the 1st interim analysis. The IDMC may request to review efficacy data if early data warrants. Decision s from the IDMC will take the nature of premature data into account unless prevailing data suggest conclusive outcome of the trial. Early safety signal will guide patient enrollment to maximize the effectiveness of treating this patient population with SCTA01.
- The 2nd interim analysis is for dose selection: the analysis will be performed at the end of Phase II when the 285th patient completed Day 29 or Early Withdraw visit. The dose selected to continue to the Phase III part will be the dose with the greater effect in reduction of viral load compared to placebo at Day 8. Time to clinical improvement of each dose will be evaluated and the RR threshold of 1.15 will be used as a futility boundary at the end of Phase II. The futility boundary is non-binding, and the IDMC may recommend study continuation

even if the futility bound is met on TTCI. If any safety signal is observed for any dose, the IDMC will weigh this information against the efficacy results in selecting the dose for Phase III.

- The 3rd interim analysis is the penultimate analysis that allows for stopping for superior efficacy. It is planned when 160 patients in Phase III (approximately 31% information time of Phase III part, which will have approximately 128 TTCI events) have been documented in the ITT population. If the interim analysis is performed at 31% of information time of Phase III, based on Pocock type boundary of α -spending function, a 1-sided p -value less than 0.01068 using inverse normal method to combine p -value from Phase II part and Phase III part will need to be observed to declare statistical significance. A futility boundary of an observed RR of 1.22 will be used to declare failure of the study when TTCI events from Phase II and Phase III part combined are exactly 280, which is equivalent to an observed one-sided p -value of 0.05.

Note: The critical values of nominal p -value and hazard ratio that will be used to declare statistical significance and/or futility at the interim analysis will be calculated based on the actual number of the TTCI events documented at the time the interim analysis.

The interim analyses will be performed by an independent statistician external to the study team. The results of the interim analyses will be presented to the IDMC by the independent statistician. The IDMC will provide the Sponsor with a recommendation to continue the trial as planned, to have an interruption, to make a protocol amendment, or to terminate the trial. If the interim analysis demonstrates significant shortening of TTCI in the SCTA01 group compared to the control group, IDMC could recommend to terminate and un-blind the study, and the study could be announced as completed.

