- The 3rd interim analysis is the penultimate analysis that allows for stopping for superior efficacy. It is planned when 160 patients in Phase III (approximately 31% information time of Phase III part, or equivalently 50% of the TTCI events combined from phase II and phase III part of the study) have been documented in the ITT population. If the interim analysis is performed at 31% of information time of Phase III, based on Pocock type boundary of α -spending function, a 1-sided p -value less than 0.01068 using inverse normal

method to combine *p*-value from Phase II part and Phase III part will need to be observed to declare statistical significance. A futility boundary of an observed RR of 1.22 will be used to declare failure of the study when TTCI events from Phase II and Phase III part combined are exactly 280, which is equivalent to an observed one-sided *p*-value of 0.05.

Note: The critical values of nominal *p*-value and hazard ratio that will be used to declare statistical significance and/or futility at the interim analyses will be calculated based on the actual number of the TTCI events documented at the time the interim analysis.

The interim analyses will be performed by an independent statistician external to the study team. The results of the interim analyses will be presented to the IDMC by the independent statistician. The IDMC will provide the Sponsor with a recommendation to continue the trial as planned, to have an interruption, to make a protocol amendment, or to terminate the trial. If the interim analysis demonstrates significantly shortened TTCI in the SCTA01 group compared to the control group, the IDMC could recommend to terminate and un-blind the study, and the study could be announced as completed.

Main Inclusion Criteria:

- Hospitalized patients with severe COVID-19 (5 point on the 8-point ordinal scale). According to the NIH definition, severe patients are those individuals who have one of the following: 1) respiratory rate > 30 breaths per minute 2) SpO₂ ≤ 93% on room air at sea level; 3) PaO₂/FiO₂ < 300 mmHg or SpO₂/FiO₂ ≤ 315 mmHg; 4) lung infiltrates > 50%. In high altitude area (over 1000 meters), PaO₂/FiO₂ should be corrected according to the following formula: PaO₂/FiO₂ × [760/barometric pressure (mmHg)]; 5 point: Hospitalized, requiring supplemental oxygen;
- Male or female adult ≥18 years of age at time of enrollment;

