9.4. Sample Size

The treatment estimates are based on the study ACTT-1 of Remdesivir[®] for COVID-19. Under the TTCI definition used in this study, rate ratio (RR) for recovery for the severe patients, the patients with 5-point of baseline ordinal score and the patients with 6-point of baseline ordinal score is 1.31, 1.45 and 1.09 respectively^{31,32}. The event rate for the patients with 5-points is 88.8% and 76.8% for Remdesivir[®] group and placebo group, respectively. The assumption to calculate the sample size is set on the results from 5-points patients, which is RR as 1.4 and event rate as 80%. The sample size determination assumptions aim at a more meaningful clinical difference under a stricter TTCI definition.

Sample size is calculated based on the following assumptions:

- Overall Type-I error rate should not exceed 2.5% (1-sided);
- Rate ratio (RR) sets to be 1.4 (if the median TTCI is 9 days on the placebo group, the SCTA01 group will be 6.5 days under the assumption of Exponential distribution);
- Randomization ratio of study drug group and placebo group in Phase III is 1:1;
- Randomization ratio of medium dose group, high dose group and placebo group in Phase II is 1:1:1;
- 80% event rate;
- Sample size ratio of Phase II and Phase III is 1:1.79;
- Simes method will be applied to attain adjusted *p*-value from Phase II;

- Inverse normal weighting method will be used to combine *p*-value from Phase II and Phase III part;
- The 3rd interim analysis, which is the penultimate analysis for superior efficacy stopping and futility analysis, will be conducted when 31% of the TTCI events have been observed from the Phase III part;
- Pocock boundary (Lan DeMets 1983) will be used to control overall Type I error within 1-sided 2.5%;
- The critical values of nominal *p*-value will be re-calculated based on the actual number of TTCI events documented at the time of interim analysis and final analysis.

The study will randomize 795 patients totally, with Phase II of 285 patients and Phase III of 510 patients (255 in each group), providing over 90% power.

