9.7.2. Multiple Testing in Adaptive Seamless Design

9.7.2.1 Combination Test

Confirmatory testing of the hypothesis comparing optimal dose with placebo using data collected from Phase II and Phase III part will use a closed testing procedure. This hypothesis will be rejected at level α (one-side 0.025) if it and all intersection hypotheses involving it are all rejected at local level α (one-side 0.025). The testing strategy used to combine results from Phase II and Phase III part will be a combination test based on the inverse normal weighting method, with the test statistic of the combination test calculated as (*Bauer and Kohne 1994*):

$$\text{Sqrt}(n_1/n)*\Phi^{-1}(1-p_1) + \text{Sqrt}(n_2/n)*\Phi^{-1}(1-p_2)$$

Where n_1 and n_2 are the sample size in Phase II and III, respectively, $n = n_1+n_2$, Φ refers to the standard normal distribution, and p_1 and p_2 are the p -value from Phase II and III, respectively. p_1 is the Simes-adjusted p -value in Phase II, and p_2 is the unadjusted p -value to compare optimal dose with placebo in Phase III.

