Interim 1(Safety review only)	NA	NA	NA	NA	NA
End of Phase II	149	NA	RR < 1.15	0.9385	0.8106
Interim 3	280	0.01068	RR < 1.22	0.9987	0.985
End of Phase III	556	0.0166	NA	0.9999	0.9897

Our simulation results suggest with the planned sample size and timing of interim analysis, under the hypothesis that SCTA01 is harmful (RR = 0.9) or has no effect (RR = 1), the probability of stopping the trial for applying a futility boundary of RR=1.15 is very probable with at least 81% probability, even at the early enrollment of the trial, e.g. the end of Phase II. Similarly, the probability of stopping the trial for applying a futility boundary of RR=1.2 is very probable with at least 88% probability.

Phase III: An unblinded interim analysis is planned.

The penultimate analysis, that allows for stopping the study for superior efficacy is planned when approximately 128 (31%) of the TTCI events have been documented in the Phase III ITT population. An α -spending function due to Lan DeMets (1983) with Pocock type stopping boundary will be used for the interim efficacy analysis. Therefore, if the interim analysis is done right after 280 events from Phase II and Phase III part have been documented, the combined *p*-value based on the inverse normal method of less than **1-side of 0.01068** will need to be observed to declare statistical significance. A futility boundary of an observed RR of 1.22 may be used to declare failure of the study when TTCI events from Phase II and Phase III part combined are exactly 280. Similarly, this more stringent than calculated futility boundary is set to control unwanted false positive rate. Note that the critical values of nominal *p*-value and hazard ratio needed to declare statistical significance at the interim analysis will be calculated based on the actual number of TTCI events documented at the time of the interim analysis.

An independent statistician external to the study team will perform the interim analyses and present the results to the IDMC. The IDMC will provide the Sponsor with a recommendation to continue the trial as planned, to have an interruption, to make a protocol amendment, or to terminate the trial. If the interim analysis demonstrates significant shorten TTCI in SCTA01 group compared to control group, the IDMC could recommend to terminate and un-blinded the study, and thus announce the study as completed.

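### Table 7 gives a 0.985 chance of stopping a null drug by the third interim; the stated rate-ratio rules give about 0.96, and the 0.05 attached to RR 1.22 is not labelled as the unadjusted pooled p

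*Combined protocol and SAP*

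**What the plan says.** The third-interim rule appears in the Synopsis, Section 3.1, Section 9.7.5 and Table 7.

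- Section 3.1, with matching text in the Synopsis: "A futility boundary of an observed RR of 1.22 will be used to declare failure of the study when TTCI events" from the two phases "combined are exactly 280, which is equivalent to an observed one-sided" p-value of 0.05.
- Section 9.7.5 softens the verb and drops the p-value: "A futility boundary of an observed RR of 1.22 may be used to declare failure of the study when TTCI events" from both phases total 280.
- The note in the Synopsis, repeated in Section 3.1, makes the threshold depend on the event count: the critical p-value and "hazard ratio that will be used to declare statistical significance and/or futility at the interim analyses will be calculated" from the events actually documented.
- Efficacy at the same look is judged by "a combination test based on the inverse normal weighting method" (Section 9.7.2.1), with a Simes-adjusted Phase II p-value. The boundary is 0.01068 at this look and 0.0166 at the end.
- Table 7 lists, for the end of Phase II at 149 events, "RR < 1.15 0.9385 0.8106": the boundary, then the stopping probability under RR = 0.9 and under RR = 1. For Interim 3 (280 events, RR below 1.22) it gives cumulative values of 0.9987 and 0.985. For the end of Phase III (556 events) it gives 0.9999 and 0.9897.

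Section 9.7.5 attributes the probabilities to simulation studies but does not describe their settings.

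**The concern.** Table 7 is the plan's evidence on how well its futility rules work. A sponsor or IDMC member reading the Interim 3 row would conclude that only 15 in 1,000 trials of an ineffective drug continue beyond that look. If the stated thresholds do not deliver that figure, then either the figure is wrong or the rule that was simulated is not the rule that was written down.

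The 0.05 adds a smaller ambiguity. The sentence just before it speaks of the inverse-normal combined p-value, and the next sentence does not say which p-value it means. The threshold is to be recalculated if the event count is not exactly 280. That needs an anchor, and the 0.05 is the only one offered.

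**Working it through.** **Inputs.** Events of 149, 280 and 556, and thresholds of 1.15 and 1.22, from Table 7; efficacy boundaries 0.01068 and 0.0166 from Section 9.3; Simes adjustment and inverse-normal weights from Section 9.7.2.1; 1:1 comparison of the selected dose with placebo. Assumption: the dose is chosen independently of TTCI (the plan chooses on Day 8 viral load).

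**Step 1: the 0.05.** With 1:1 allocation, z = ln(RR) × √d / 2.
- RR 1.22, d = 280: 0.1989 × 16.733 / 2 = 1.664, one-sided p = 0.048.
- Inversely, p = 0.05 gives RR = exp(2 × 1.645 / √280) = 1.217, which rounds to 1.22.

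The plan's equivalence reproduces for the unadjusted pooled log-rank test.

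**Step 2: the same RR on the combined p.** Take RR 1.22 in both phases, with 149 and 131 events (280 − 149 = 131). Phase II: z = 1.214, p = 0.112. Phase III: z = 1.138.
- If both doses have the same Phase II p, Simes adds nothing. The combined p is 0.051 (weights 285/795 and 510/795) or 0.054 (190/700 and 510/700).
- If the other dose shows RR 1, the Simes p is 2 × 0.112 = 0.225 and the combined p is 0.086 with either set of weights.
- Holding the pooled RR at 1.22 while the Phase II RR moves from 1.15 to 1.40 takes the combined p from about 0.04 to 0.13, depending on weights and the Simes penalty.

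So no single combined p corresponds to a pooled RR of 1.22.

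**Step 3: Table 7 under RR = 1.**
- End of Phase II: z = ln(1.15) × √149 / 2 = 0.853; Φ = 0.803 (stated 0.8106).
- Interim 3 alone: Φ(1.664) = 0.952.
- The two statistics correlate at √(149/280) = 0.730, so the probability of being below both thresholds is 0.794.
- Cumulative futility: 0.803 + 0.952 − 0.794 = 0.961 (stated 0.985).

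Using 152 Phase II events (190 × 0.8) instead of 149 also gives 0.960. Simulations of 2 to 3 million trials with two doses sharing placebo give 0.960 to 0.961; patient-level simulations give 0.960 and 0.966. Counting efficacy stops as well gives 0.966 to 0.967. Final non-rejection is 0.990 (stated 0.9897).

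**Step 4: Table 7 under RR = 0.9.** The same calculation gives 0.933 (stated 0.9385) and 0.9957 (stated 0.9987). Final non-rejection by simulation is 0.9996 (stated 0.9999).

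**Step 5: what might give 0.985 under RR = 1?**

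| Variant | Cumulative at Interim 3 |
|---|---|
| RR < 1.2 at end of Phase II (alternative in Section 9.7.5), then 1.22 | 0.966 |
| RR < 1.22 on Phase III data only | 0.975 |
| Both doses must fall below 1.15 at Phase II | 0.958–0.959 |
| Dose with better TTCI selected | 0.935 |
| Combined p > 0.05 instead of RR < 1.22 | 0.975–0.977 |
| The same, plus efficacy stops | 0.981–0.982 |
| Pooled RR < 1.29 (unadjusted p about 0.017) | 0.985 |

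None of the variants that keep RR < 1.22 reaches the stated figure.

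**The case against.** The strongest reply is that the plan's arithmetic on the 0.05 is right, and this stands. A reader might infer that the plan wrongly equates RR 1.22 with the Simes-adjusted combined p. The documents do not support that. The efficacy sentence names the inverse-normal method; the futility sentence does not, and nowhere is the 0.05 called combined or adjusted. The operative rule is stated as a rate ratio in every place, with the p-value as a gloss. It follows that there are not two competing stopping rules, and rates of disagreement between an RR rule and a combined-p rule would measure a conflict the plan does not create. What is missing is a label.

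On Table 7, the reply is that the simulation settings are undisclosed and cumulative stopping is undefined. With efficacy stops counted, the gap is just under 2 percentage points, and the RR = 0.9 entry is only 0.3 points off. This is fair as to size and cause. But the final-row entry under RR = 1 is below 1 and matches non-rejection, so the column appears to count futility and failure, not every stop. On that reading the gap is 2.4 points, in a row whose neighbours reproduce to within 0.8 points. Reading futility as combined p > 0.05 comes closer, but that is not the rule printed in the row.

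Futility stopping cannot inflate the type I error, and the IDMC only recommends. Both points stand and limit the consequence.

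**Conclusion.** The Interim 3 row of Table 7 is wrong as written for the rule printed beside it. Under RR = 1 the stated rules stop about 0.961 of trials by this look (0.966 to 0.967 with efficacy stops), against 0.985. A null drug continues in about 3.3 to 3.9% of trials rather than 1.5%, more than twice the implied rate. Under RR = 0.9 it is about 0.4% against 0.13%. This rests on normal approximations at the planned event counts and on dose selection unrelated to TTCI. The cause of the gap cannot be identified from the documents.

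The 0.05 is correct as a nominal unadjusted pooled p and needs only to be named as such. It would also be tempting to conclude that the design's error control or power is compromised; nothing here shows that, and the final-row value under RR = 1, which carries the overall false-positive rate, reproduces.

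**What to change.** 1. Rerun the Interim 3 row of Table 7 for RR < 1.15 at 149 events followed by RR < 1.22 at 280, and restate it: about 0.96 to 0.97 under RR = 1 and about 0.996 under RR = 0.9. If 0.985 came from a different rule or setting, correct the rule or settings in the text instead. Either way, state whether the column includes efficacy stops and give the simulation settings.
2. In the Synopsis and Section 3.1, label the 0.05 as the nominal unadjusted one-sided p of the pooled log-rank test, and make it the anchor for other event counts: threshold = exp(2 × 1.645 / √d). That is 1.226 at 260 events, 1.217 at 280 and 1.209 at 300.
3. Use one verb for the rule in the Synopsis, Section 3.1 and Section 9.7.5, so that it is clear whether the boundary will or may be applied.

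The cost is wording in three places and a rerun of one table row. The restated probability is slightly less favourable; boundaries, alpha and sample size do not change if the RR rule is kept.

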3.2. Number of Subjects

Up to 795 patients will be randomized for this Phase II/III study.

3.3. Duration of Treatment

Single dose of drug.

3.4. Premedication for Infusion

Premedication for infusions is not planned. However, if the participant has a medical history suggesting a potential benefit from premedication, the study investigator (s) should determine the appropriate premedication. The investigators and sponsor may decide to use premedication if the frequency of infusion reactions among participants warrants it.

If minor infusion reactions are observed, administration of acetaminophen, antihistamines and/or other appropriately indicated medications may be given prior to the start of infusions for subsequent participants.

The decision to implement premedication for infusions in subsequent participants will be made by the investigator and sponsor and recorded in the study documentation.

Any premedication given will be documented as a concomitant therapy.

3.5. Dose Modification

No dose modification is needed.

All subjects should be monitored closely for infusion-related reactions and anaphylaxis for at least 2 hours after the completion of the infusion. Emergency equipment and medication for the treatment of infusion-related reactions and anaphylaxis must be available for immediate use during the infusion and the post-infusion monitoring period if required for treatment.

Sites should have appropriately trained medical staff to recognize and treat infusion-related reaction and anaphylaxis. It is recommended that participants who experience an infusion-related reaction or anaphylaxis can be treated per the local standard of care.

The infusion can be reduced to 50% of the infusion rate / interrupted then be restarted at 50% of the original rate if any of the following adverse events are observed:

- Sustained/severe cough
- Rigors/chills
- Rash, pruritus (itching)
- Urticaria (hives, welts, wheals)
- Diaphoresis (sweating)
- Hypotension
- Dyspnea (shortness of breath)
- Vomiting
- Flushing

If investigators feel there is a medical need for treatment or discontinuation of the infusion other than described above, they should use clinical judgment to provide the appropriate response according to standard clinical practice.

The infusion should be terminated and not restarted if any of the following adverse events occur:

- Anaphylaxis*
- Laryngeal/pharyngeal edema
- Severe bronchospasm
- Seizure
- Severe hypotension
- Other neurological symptoms (confusion, loss of consciousness, paresthesia, paralysis, etc)
- Any other symptom or sign that, in the opinion of the investigator, warrants termination of the

intravenous infusion

*Consider anaphylaxis if the following is observed ²⁷: acute onset of an illness (minutes to several hours) with involvement of the skin, mucosal tissue, or both (eg, generalized hives, pruritus or flushing, swollen lips-tongue-uvula) and **at least one of the following**:

- Respiratory compromise (eg, dyspnea, wheeze-bronchospasm, stridor, reduced peak expiratory flow, hypoxemia)
- Reduced blood pressure or associated symptoms of end-organ dysfunction (eg, hypotonia [collapse], syncope, incontinence).

